8.1.2 Data Collected in the Conversion Period

The AE data are collected on a weekly basis on the de novo subjects that participated in the 1- to 4-week conversion period.

A TEAE in the conversion period is defined as an AE that starts after the first dose of IMP upon entering the conversion period, or an AE that is present at the baseline of the conversion period and increases in intensity or becomes serious or IMP-related or results in death, discontinuation, interruption, or reduction of the IMP.

Note that a Kaplan-Meier curve for time to discontinuation of the IMP due to AEs or death will not be plotted for the conversion period, due to the shorter length of the period and an anticipated small number of de novo subjects entering the cross-titration conversion period.

8.2 Secondary Safety Outcomes

8.2.1 Clinical Laboratory Data

A data summary will be provided for the 24-month open-label treatment period only, since there is no assessment of the clinical laboratory parameters in the conversion period.

During the 24-month open-label treatment period, clinical laboratory assessments in the fields of hematology, serum chemistry (including prolactin, glycosylated hemoglobin [HbA1c], and thyroid-stimulating hormone [TSH]), and urinalysis will be conducted at the following scheduled visits: Week 4 and Months 6, 12, 18, and 24. Refer to Table 3.7.3.2-1 of the protocol for a comprehensive list of laboratory tests (such as hemoglobin, aspartate aminotransferase [AST], alanine aminotransferase [ALT], etc) conducted in this trial.

Assessment values and the change-from-baseline values in each laboratory test will be summarized on the observed case (OC) data by visit by using the descriptive statistics for continuous variables. Refer to [Section 10.6](#) regarding descriptive statistics. Summary statistics will also be computed on the LOCF data for the last assessment visit.

The incidence of potentially clinically significant abnormal lab results will also be summarized. Refer to Appendix 2 of the protocol for the criteria for identifying laboratory values of potential clinical relevance. Data of laboratory test values with potential clinical relevance will be displayed in a data listing by subject, laboratory test, and visit.

Shift tables will be produced assessing status (low-normal-high) changes from baseline. The incidence of prolactin results $> 1 \times$ the upper limit of normal (ULN), $> 2 \times$ the ULN, and $> 3 \times$ the ULN will also be provided by gender.

An occurrence of potential serious hepatotoxicity (also referred to as potentially drug-induced liver injury) is defined as having concurrently met the following 2 criteria (ie, at the same visit) during the 24-month open-label treatment period:

- 1) ALT or AST $\geq 3 \times$ the ULN or $3 \times$ the baseline/screening value.
- 2) Increase in bilirubin $\geq 2 \times$ the ULN or $2 \times$ the baseline/screening value.

The incidence of potential serious hepatotoxicity will be summarized on the OC data by the specified visit as well as for the overall open-label treatment period. For the statistical summary of the overall open-label treatment period, the subject will be counted only once if he or she has multiple incidences of potential serious hepatotoxicity.

A by-subject listing of data of laboratory abnormalities that signal potential serious hepatotoxicity will also be provided.

Incidence of treatment-emergent potentially clinically relevant change in glucose and lipids will be summarized. The numerator in the incidence of treatment-emergent PCR is the number of subjects with 1 post-baseline potentially clinically relevant test abnormality observation (over the entire trial period) and their baseline values are normal or missing for a parameter; and the denominator is the total number of subjects with at least 1 post-baseline numeric laboratory results.

The criteria for treatment-emergent potential clinical relevance of glucose and lipids are provided in Appendix 1.

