### **3.5.2      Secondary Endpoints**

#### **3.5.2.1      Secondary Safety Endpoints**

The secondary safety endpoints are as follows:

- Mean change from baseline and incidence of clinically significant abnormalities in clinical laboratory tests and urinalysis results (including fasting blood lipids, glucose and insulin, serum prolactin, glycosylated hemoglobin [HbA1c] and creatine phosphokinase [CPK]), vital signs (supine and standing positions), weight, height, body mass index (BMI), waist circumference, and ECG parameters
- Mean change from baseline on the Abnormal Involuntary Movement Scale (AIMS), Simpson-Angus Scale (SAS), and Barnes Akathisia Rating Scale (BARS)
- Analysis of potential suicide events recorded on the Columbia-Suicide Severity Rating Scale (C SSRS)

- Comprehensive psychotropic side effects as assessed by Udvalg for Kliniske Undersøgelser (UKU) side effect rating scale
- The frequency of symptom items for the clinician-administered New York Assessment for Adverse Cognitive Effects of Neuropsychiatric Treatment: (NY-AACENT)
- Baseline and postbaseline Tanner Staging Scale data
- Time to discontinuation due to AE

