### **3.7.1.1.2.3 Baseline (Open-label Treatment Period)**

If the subject is found to be eligible for the trial during the screening/conversion period, the subject will attend a baseline (Day 1) visit for the open-label treatment period. For subjects that participated in the conversion period, the baseline (Day 1) visit of the open-label treatment period will coincide with the end of the conversion period which is up to 4 weeks in duration. The following procedures will be completed during the baseline (Day 1) visit of the open-label treatment period, prior to the subject starting open-label IMP:

- Inclusion/exclusion criteria will be reviewed.
- Prior medications will be reviewed.
- A qualified and certified rater will administer the PANSS.
- A qualified rater will administer the CGI-S.
- A qualified rater will administer the CGAS.
- The investigator (or qualified designee) will administer the SAS, AIMS, and BARS.
- The investigator (or qualified designee) will complete the “Since Last Visit” version of the C-SSRS form.
- The investigator (or qualified designee) will administer the UKU and NY-AACENT.
- Body weight, height, and waist circumference will be recorded.
- Vital sign measurements (including blood pressure, pulse and body temperature) will be recorded. Blood pressure and pulse are to be measured in the following order: supine, sitting, and standing after the subject has been in each position at least 3 minutes. Vital signs are to be completed before any blood is drawn.
- Blood samples will be collected for clinical laboratory tests (hematology and serum chemistry [including prolactin, HbA1c, and TSH]) after a minimum 8-hour fast. Vital sign and ECG assessments should be completed before any blood samples are collected.

- A standard 12-lead ECG will be performed predose after the subject has been supine and at rest for at least 5 minutes. The ECG is to be completed before any blood is drawn.
- Urine will be collected for urinalysis and from all potential subjects for urine screen(s) for drugs of abuse.
- A urine pregnancy test will be performed predose for all females. The result must be negative prior to dosing.
- A serum pregnancy test will be collected for all females.
- AEs and concomitant medications will be recorded.

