#### **3.7.1.2.1 Weeks 1, 2, and 4**

The following evaluations will be performed at Weeks 1, 2, and 4 visits:

- A qualified rater will administer the CGAS.
- The investigator (or qualified designee) will complete the “Since Last Visit” C-SSRS form.
- The investigator (or qualified designee) will administer the SAS, AIMS, and BARS.
- The investigator (or qualified designee) will administer the UKU and NY-AACENT.
- Body weight and waist circumference will be recorded.
- Vital sign measurements (including blood pressure, pulse, and body temperature) will be recorded. Blood pressure and pulse are to be measured in the following order: supine, sitting, and standing after the subject has been in each position at least 3 minutes. Vital signs are to be completed before any blood is drawn.
- Urine will be collected from all potential subjects for urine screen(s) for drugs of abuse. Urinalysis will be performed at Week 4.

- A urine pregnancy test will be performed for all females. The result must be negative prior to dosing. If the urine pregnancy test is positive at Weeks 1 or 2, the result should be confirmed with a serum pregnancy test if a serum pregnancy test is not being performed during that visit. Additional urine pregnancy testing may be done at the discretion of the investigator.
- AEs and concomitant medications will be recorded.
- A qualified and certified rater will administer the PANSS (Week 4 only).
- A qualified rater will administer the CGI-S and CGI-I (Week 4 only).
- A standard 12-lead ECG will be performed after the subject has been supine and at rest for at least 5 minutes. The ECG is to be completed before any blood is drawn (Week 4 only).
- Blood samples will be collected for clinical laboratory tests, including hematology and serum chemistry (with prolactin, HbA1c, and TSH). Blood will be drawn after a minimum 8-hour fast, if at all possible (see [Section 3.7.3.2](#)). See [Table 3.4.3.2-1](#) for exclusions based on outcome of screening clinical laboratory tests (Week 4 only).
- A serum pregnancy test will be performed for all females. Subjects with a positive serum test result will be excluded from the trial (Week 4 only).
- The IMP will be dispensed to the subject.

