### **3.7.3.2 Clinical Laboratory Assessments**

[Table 3.7.3.2-1](#) presents the protocol-required clinical laboratory test for all subjects in this trial. A central laboratory designated by the sponsor will be used for all laboratory testing required during the trial. The central laboratory should be used for all laboratory testing whenever possible (including unscheduled and follow-up laboratory tests, if needed). In cases where an immediate result is required for a particular laboratory test, the sample should be divided and sent to both a local laboratory and the designated central laboratory. Urine will be collected and blood will be drawn from each subject during screening prior to treatment with IMP and then at the scheduled visits designated in [Table 3.7-1](#) (rollover subjects from Trial 331-10-234) and [Table 3.7-2](#) (de novo subjects). The results of these tests must be reviewed by the investigator prior to initiation of IMP. Additional urine and blood samples may be collected for further evaluation of safety as warranted by the investigator's judgment. Subjects must be fasting for a minimum of 8 hours prior to blood draws for screening laboratory assessments, if at all possible. If fasting blood samples are not feasible at screening, nonfasting blood samples may be obtained initially for determining eligibility for the trial. If a subject is not fasting at a visit, the blood draw should still be performed and the status documented as nonfasting on the laboratory requisition sheet. The central laboratory will provide laboratory results to the sponsor electronically.

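### SAP 8.2.1 summarises glucose and lipid change on all samples whatever their fasting status, so the tables do not estimate the fasting endpoint of Protocol 3.5.2.1; the direction and size of the error are unknown

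*SAP*

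**What the plan says.** **Endpoint.** Protocol 3.5.2.1 asks for mean change from baseline and for the incidence of clinically significant abnormalities in laboratory tests, "including fasting blood lipids, glucose and insulin, serum prolactin, glycosylated hemoglobin [HbA1c] and creatine phosphokinase [CPK" among them.

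**Sampling.** Protocol 3.7.3.2 sets one rule for every visit: "If a subject is not fasting at a visit, the blood draw should still be performed and the status documented as nonfasting". Nonfasting values are thus expected in the database, with a marker that identifies them.

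**Visit instructions.** For de novo subjects on Day 1 (Protocol 3.7.1.1.2.3) the fast is unqualified: "Blood samples will be collected for clinical laboratory tests (hematology and serum chemistry [including prolactin, HbA1c, and TSH]) after a minimum 8-hour fast". Month 12 and Month 24/early termination are also unqualified. At Week 4 the text is softer: "Blood will be drawn after a minimum 8-hour fast, if at all possible". De novo screening, Month 6 and Month 18 carry the same qualification.

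**Analysis.** SAP 8.2.1 states: "Assessment values and the change-from-baseline values in each laboratory test will be summarized on the observed case (OC) data by visit". It adds: "Summary statistics will also be computed on the LOCF data for the last assessment visit". It also plans low-normal-high shift tables. None of the three has a fasting condition, and the SAP's baseline, windowing and last-visit rules (7.1, 10.2, 10.5) supply none.

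**Where fasting is respected.** Protocol Appendix 2 has separate fasting and nonfasting glucose limits and labels its lipid limits fasting. SAP Appendix 1 labels its glucose and lipid criteria fasting.

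**The concern.** The mean-change half of the endpoint concerns fasting values, while the tables meant to deliver it pool all values. Once nonfasting samples enter, a by-visit change combines any true metabolic change with a change in the mix of samples, and a reader of the table cannot separate the two.

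This matters because the trial is single-arm. There is no concurrent control in which the same mixing would occur and largely cancel, so the descriptive change over time is the main evidence on average metabolic effect. The protocol itself describes adolescents as more sensitive to antipsychotic side effects, weight gain in particular.

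Two SAP rules widen the exposure. Under 10.2, unscheduled laboratory results are mapped to an analysis visit and the last observation in the window is used, so a later nonfasting draw can displace a scheduled fasting one. Under 7.1.1, a de novo baseline is the last value before the first open-label dose, so it can fall back to a screening sample, where the fast is only qualified.

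**Working it through.** The plan states no figure to reproduce: the sample size is not power-based and no nonfasting rate is given. The check therefore covers what determines the error and whether its sign is fixed.

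**1. Fasting instruction by time point**

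| Time point | Instruction in the protocol |
|---|---|
| Rollover baseline (parent trial Week 6) | not in these documents |
| De novo screening (possible fallback baseline) | qualified |
| De novo Day 1 | unqualified |
| Week 4 | qualified |
| Month 6 | qualified |
| Month 12 | unqualified |
| Month 18 | qualified |
| Month 24/ET | unqualified |

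The wording is softer at three of the five scheduled postbaseline laboratory visits. Because 3.7.3.2 allows a nonfasting draw at any visit, unqualified wording does not guarantee a fasting sample.

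**2. Formula.** Let D be the nonfasting-minus-fasting difference for an analyte, p_base the nonfasting share at baseline and p_post the share at the visit. If D is the same at both times and unrelated to who attends nonfasting, then

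error in mean change = D × (p_post − p_base).

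**3. Assumed ranges.** D = 10, 20 or 40 mg/dL; p_post = 5% to 30%; p_base = 0% to 30%. All are assumptions.

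- All baselines fasting (p_base = 0):
  - D = 10: 10 × 0.05 = +0.5 to 10 × 0.30 = +3.0 mg/dL
  - D = 20: +1.0 to +6.0 mg/dL
  - D = 40: +2.0 to +12.0 mg/dL
- Equal shares: D × 0 = 0 for any D.
- More nonfasting at baseline:
  - D = 20, p_base = 30%, p_post = 10%: 20 × (0.10 − 0.30) = −4.0 mg/dL
  - D = 40, p_base = 30%, p_post = 5%: 40 × (0.05 − 0.30) = −10.0 mg/dL

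**4. Mixed cohort.** Take D = 20, p_post = 20%, 20% of subjects de novo, and all de novo baselines fasting.

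- 30% of rollover baselines nonfasting: p_base = 0.80 × 0.30 = 0.24, so the error is 20 × (0.20 − 0.24) = −0.8 mg/dL.
- No rollover baselines nonfasting: 20 × (0.20 − 0) = +4.0 mg/dL.

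The sign therefore turns on the fasting status of the rollover baselines, which these documents do not give. For an analyte with negative D, every sign reverses.

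**5. After the fix.** With documented fasting pairs only, p_base = p_post = 0 and the term is D × 0 = 0 for any D.

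The formula covers means. The shift tables have the same mixture, but their error cannot be sized this way.

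**The case against.** The strongest reply is that much of this is already handled and the rest is small. The incidence half of the endpoint uses fasting-labelled criteria. HbA1c is also summarised and gives a partial cross-check on glucose. Weight, BMI and waist do not depend on the fasting flag. No inferential analysis is planned, and no decision threshold hangs on these means. All of that stands, and it limits the point to the mean-change, last-visit and shift tables for glucose and lipids. It does not supply a fasting rule for those tables.

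A reader might infer stronger conclusions that the documents do not support:

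- **That mean changes are biased upward.** This needs a larger nonfasting share after baseline than at baseline, and an analyte that is higher when nonfasting. The visit wording points that way only for de novo subjects with a Day 1 sample. The fasting rule for the rollover baseline is not given. Under SAP 7.1.1, subjects delayed by the COVID-19 enrolment pause who enter without conversion also take Week 6 values.
- **That the profile will dip at Months 12 and 24.** This is possible but not shown. Nonfasting draws are allowed at those visits too, the schedules of assessments make no fasting distinction by visit, and the qualified text at Week 4 and Month 18 also repeats a cross-reference to screening exclusions, so it may be carried-over wording.
- **That the error can be judged against the 10 mg/dL glucose rise in SAP Appendix 1.** That criterion applies to individual subjects and is labelled fasting. A shift in a group mean is a different quantity.

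A fair point against the remedy is that requiring fasting at both times removes subjects, and the documents do not show how many.

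**Conclusion.** The concern holds in limited form. As written, SAP 8.2.1 mixes fasting and nonfasting glucose and lipid values in the by-visit, last-visit and shift tables, although fasting status is recorded. To the extent nonfasting samples occur, those tables do not estimate the fasting change named in Protocol 3.5.2.1.

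Direction and size are unknown and may differ by visit, analyte and cohort. The −10.0 to +12.0 mg/dL span rests wholly on the assumed inputs and includes zero. It shows that the sign is open; it does not predict the error. The primary adverse-event endpoints and the fasting-labelled threshold tables are outside this point. The SAP should be corrected before the final analysis because, without the split, a reader cannot tell a zero error from a material one.

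**What to change.** In SAP 8.2.1, for glucose, triglycerides and total, LDL and HDL cholesterol:

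- Base the by-visit, last-visit and shift summaries on samples documented as fasting at both baseline and the postbaseline visit.
- For the last visit, use the last fasting postbaseline value, and note this exception in SAP 10.5, which otherwise takes the Month 24 or early-termination value.
- Keep the all-sample summaries as supportive tables.
- Report nonfasting and unknown-status counts by visit, separately for rollover and de novo subjects.
- State how unknown status is handled.

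This needs SAP wording and a filter on a status that sites already record; no new data are collected. The price is fewer evaluable pairs for these five analytes, by a number the documents do not allow one to compute, and an earlier last-visit value for subjects whose final sample is nonfasting. Subjects with fasting pairs may also differ from the rest, which is a reason to keep the all-sample tables alongside.

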| Non-Fasting                |  | $\geq 200$ mg/dL   |
| Total Cholesterol, Fasting |  | $\geq 240$ mg/dL   |
| LDL Cholesterol, Fasting   |  | $\geq 160$ mg/dL   |
| HDL Cholesterol, Fasting   |  |  |
| Men                        |  | $< 40$ mg/dL   |
| Women                      |  | $< 50$ mg/dL   |
| Triglycerides, Fasting     |  | $> 150$ mg/dL  |

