7.1 Definition of the Baseline Value

7.1.1 Baseline for the 24-month Open-Label Treatment Period

Subjects entering the 24-month open-label treatment period come from three sources: (1) rollover subjects, (2) de novo subjects who skipped over a cross-titration conversion period and directly entered the open-label treatment period, and (3) de novo subjects who were required to participate in the conversion period to achieve a brexpiprazole monotherapy target starting dose of 1, 2, or 3 mg daily at any time after Week 1, and to achieve the required washout of prohibited medications. Once these goals have been achieved as deemed by the investigator, the subject will proceed to the baseline (Day 1)

visit of the open-label treatment period. It is possible that some de novo subjects cannot achieve these goals and thus will not enter the open-label treatment period.

For rollover subjects, baseline for the 24-month open-label treatment period is simply defined as the assessment value taken on the subject at the last visit (ie, the Week 6 visit) of the double-blind treatment period of the parent trial, whereas for de novo subjects (regardless of participating in the conversion period or not), baseline is defined as the last assessment value prior to the first dose of IMP upon entering the 24-month open-label treatment period. In other words, for de novo subjects, the data imputation rule last observation carried forward (LOCF) applies in determining the baseline value pertinent to the open-label treatment period. Note that there will be no imputation of baseline values for rollover subjects.

Note that there could be a small subset of subjects who completed the parent trial but could not directly rollover to the current trial due to the COVID-19 pandemic related pause of enrollment. These impacted subjects may be allowed to enroll later on as de novo subjects into the current trial (as mentioned in [Section 3](#)). If such a de novo subject enters the open-label treatment period without undergoing a conversion period, then his or her baseline values for the open-label treatment period will simply be the same as the assessments collected at the last visit (ie, the Week 6 visit) of the parent trial.

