10.8 Other Conventions

Percentage change from baseline is calculated as the change from baseline divided by the baseline value, then multiplied by 100. If the baseline value is zero, the percentage change will be undefined. If the baseline value is missing, the percentage change from baseline will be missing.

The International System of Units (Système international d'unités or SI) is the current international standard metric system. The SI units will be used for the reporting in all tables/figures/listings for this trial.

11 References

- ¹ Otsuka Pharmaceutical Development & Commercialization, Inc. A long-term, multicenter, open-label trial to evaluate the safety and tolerability of flexible-dose brexpiprazole as maintenance treatment in adolescents (13-17 years old) with schizophrenia. Otsuka Protocol 331-10-236, issued 04 May 2017, amended 01 Dec 2017, 13 Sep 2018, 03 Jun 2019, 16 Jun 2020, and 04 Aug 2021.
- ² Otsuka Pharmaceutical Development & Commercialization, Inc. Multicenter, randomized, double-blind, placebo- and active-controlled trial to evaluate the efficacy of brexpiprazole monotherapy for the treatment in adolescents (13-17 years old) with schizophrenia. Otsuka Protocol 331-10-234, issued 10 Mar 2017, amended 24 Aug 2018, 31 May 2019, 16 Jun 2020, and 05 Jul 2022.

Appendix 1**Criteria for Metabolic Change****Incidence of Treatment-Emergent Significant Change in Lipids**

Parameters	Baseline	Anytime post baseline
Total Cholesterol, fasting (mg/dl)	Normal < 170	High \geq 200
	Borderline 170 - < 200	High \geq 200
	Normal/Borderline < 200	High \geq 200
	Normal < 170	Borderline/High \geq 170
LDL-cholesterol, fasting (mg/dl)	Normal < 110	High \geq 130
	Borderline 110 - < 130	High \geq 130
	Normal/borderline < 130	High \geq 130
	Normal < 110	Borderline/High \geq 110
HDL-cholesterol, fasting (mg/dl)	Normal > 45	Low < 40
	Borderline 45 - \geq 40	Low < 40
	Normal/Borderline \geq 40	Low < 40
	Normal > 45	Borderline/Low \leq 45
Triglycerides, fasting (mg/dl)	Normal < 90	High \geq 130
	Borderline 90 - < 130	High \geq 130
	Normal/borderline < 130	High \geq 130
	Normal < 90	Borderline/High \geq 90

Incidence of Treatment-Emergent Significant Change in Glucose

Parameters	Baseline	Anytime post baseline
Glucose fasting, serum (mg/dl)	Normal < 100	High \geq 126
	Impaired 100 - < 126	High \geq 126
	Normal/impaired < 126	High \geq 126
	Any Value	increased \geq 10

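### The rule for treatment-emergent glucose and lipid incidence has a mismatched numerator and denominator and does not fit the 20 baseline-specific rows of SAP Appendix 1

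*SAP*

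**What the plan says.** SAP 8.2.1 (Clinical Laboratory Data) defines the incidence of treatment-emergent, potentially clinically relevant change in glucose and lipids. A subject enters the numerator if a post-baseline abnormality occurs at any time in the trial and "their baseline values are normal or missing for a parameter". For the other half of the fraction, "the denominator is the total number of subjects with at least 1 post-baseline numeric laboratory results". The criteria are then referred to SAP Appendix 1.

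Appendix 1 has 20 rows, and each names a baseline category as well as a post-baseline criterion. Some start from a non-normal baseline, for example "Borderline 170 - < 200" for total cholesterol and "Impaired 100 - < 126" for glucose. Every parameter in the appendix is a fasting one.

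Three other provisions bear on this:
- SAP 7.1.1, on baselines: "Note that there will be no imputation of baseline values for rollover subjects".
- Protocol 3.7.3.2, on sampling: "If a subject is not fasting at a visit, the blood draw should still be performed", with non-fasting status noted on the laboratory requisition.
- SAP 10.6 has a default denominator of subjects at risk, but it yields wherever another rule is specified, as it is here.

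**The concern.** An incidence of emergence needs a numerator drawn from the denominator's at-risk group. Here the numerator is restricted by baseline and the denominator is not. The single restriction to normal or missing baselines also contradicts the Appendix 1 rows that start from borderline, impaired, combined or any baseline values. Two programmers could reasonably produce different tables from the same data.

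Two further mismatches follow. A subject with a missing baseline counts as emergent although emergence cannot be shown. And the criteria are fasting, while the denominator accepts any numeric result.

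Abnormalities in fasting lipids and glucose are a named secondary safety endpoint (protocol 3.5.2.1), and SAP 8.1 lists effects on glucose and on lipids as topics of interest. SAP 10.7 shows results in five columns: four prior-treatment groups and all subjects. If baseline mix differs between groups, equal true risks will appear as different percentages.

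**Working it through.** The plan states no rate for this table, so there is no figure to reproduce. The check has two parts: a row count, which needs no assumptions, and an illustration of size, which does.

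**Row count.** Each lipid (total cholesterol, LDL, HDL, triglycerides) has two Normal rows, one Borderline row and one Normal/Borderline row. Glucose has one row each for Normal, Impaired, Normal/impaired and Any Value. Total: 4 × 4 + 4 = 20.

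| Baseline category of row | Rows | Under the literal numerator |
|---|---|---|
| Borderline or Impaired | 4 + 1 = 5 | No subject with an observed baseline in the category can be counted |
| Normal/Borderline, Normal/impaired, Any Value | 4 + 1 + 1 = 6 | Events from non-normal baselines are dropped |
| Normal | 8 + 1 = 9 | Numerator fits, but the denominator includes subjects not at risk |

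This sorts each row by its main defect. Counting denominators alone, 19 of the 20 are wider than the row's category; only glucose Any Value is not.

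**Illustration.** All inputs are assumed. Risk of being High post-baseline: pN = 0.10 from normal, pB = 0.40 from borderline, pH = 0.90 from already high. Baseline shares are sN/sB/sH, with no missing baselines at first.

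- Normal to High, reported: sN × pN.
- Borderline to High, reported: 0 literally; sB × pB if the row's own category sets the numerator but everyone is in the denominator.
- Normal/Borderline to High, true: (sN × pN + sB × pB)/(sN + sB). Reported: sN × pN literally; sN × pN + sB × pB with the row's own category in the numerator.

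| | 90/8/2% | 70/20/10% | 50/30/20% |
|---|---|---|---|
| Normal to High, true 10%: reported | 9% | 7% | 5% |
| Borderline to High, true 40%: literal | 0% | 0% | 0% |
| Same, row-specific numerator over everyone | 3.2% | 8% | 12% |
| Normal/Borderline to High: true | 12.4% | 16.7% | 21.3% |
| Same, literal | 9% | 7% | 5% |
| Same, row-specific numerator over everyone | 12.2% | 15% | 17% |

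**Missing baselines.** Let m be the share missing, and pM = sN × pN + sB × pB + sH × pH = 0.14, 0.24, 0.35 for the three share sets. The Normal row then reports sN(1 − m)pN + m × pM.

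- m = 0.10: 9.5, 8.7, 8.0%.
- m = 0.20: 10.0, 10.4, 11.0%.

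The reported rate passes the true 10% at m = (1 − sN)pN/(pM − sN × pN) = 0.01/0.05, 0.03/0.17, 0.05/0.30 = 0.20, 0.18, 0.17. With pH = 0.50 instead, pM = 0.132, 0.20, 0.27, and the crossing is at 0.01/0.042, 0.03/0.13, 0.05/0.22 = 0.24, 0.23, 0.23.

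**Fasting.** If only 80 to 90% of the denominator had a post-baseline fasting result (assumed), the 7% above becomes 0.8 × 7 = 5.6% to 0.9 × 7 = 6.3%.

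**Columns.** A true 10% Normal-to-High risk in two groups with 80% and 60% normal baselines is reported as 8% and 6%.

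**Other tables.** SAP 8.2.1 also promises change from baseline and incidence by protocol Appendix 2, and says "Shift tables will be produced assessing status (low-normal-high) changes from baseline". None of these uses the Appendix 1 categories. The fasting cut-offs (mg/dL) compare as follows:

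| | Protocol Appendix 2 | SAP Appendix 1, High (Low for HDL) |
|---|---|---|
| Total cholesterol | ≥ 240 | ≥ 200 |
| LDL | ≥ 160 | ≥ 130 |
| Triglycerides | > 150 | ≥ 130 |
| Glucose | ≥ 100 | ≥ 126 |
| HDL | < 40 men, < 50 women | < 40 |

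**The case against.** The strongest reply is that the 5/6/9 split depends on reading the word normal in 8.2.1 as the Appendix 1 label. A sensible programmer would apply the baseline column printed beside each row, and then no row is empty or incomplete. That is fair. But nothing in the SAP says that the column overrides the text, and the denominator remains too wide in 19 of 20 rows.

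A second reply is that a crude proportion among all subjects with post-baseline data is a legitimate, explicitly stated quantity, and that the 9 Normal rows can be run exactly as written. They can, but the result is not an incidence among those at risk, and it shifts with baseline mix. Counting missing baselines as emergent is also a stated choice that favours reporting more events; that does not make those cases demonstrably emergent.

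Third, the fasting restriction might be inferred because Appendix 1 names its parameters as fasting, and the protocol asks for an 8-hour fast at de novo Day 1, Month 12 and Month 24. The denominator wording does not say so.

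Some of the case against does stand. For glucose and HDL, every High or Low value under Appendix 1 also meets the protocol Appendix 2 criterion, so those abnormalities remain visible elsewhere, though emergence is not isolated there. Missingness as high as 17 to 24% has no support in the documents, because baseline laboratory tests are scheduled for everyone. No inferential comparison between columns is planned.

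**Conclusion.** The concern holds. The rule in SAP 8.2.1 cannot be applied consistently to the rows of Appendix 1, and under either reading of the numerator the denominator is too wide in 19 of 20 rows. That part rests on the text alone.

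The size depends on baseline shares and risks that the documents do not give. Across the assumed range, a Normal-to-High rate falls from 10% to between 9% and 5%, and the Borderline-to-High row is lost under the literal rule. With no missing baselines the literal rule understates the rates whenever non-normal baselines are present (for the Any Value row, whenever those subjects have events). Missing baselines work in the opposite direction, so no single direction of bias can be claimed.

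The effect is limited to one descriptive secondary safety table. The primary endpoints, sample size and data collection are untouched. It should be fixed, but it does not threaten the trial's main conclusions.

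**What to change.** For each row of SAP Appendix 1:
- **Denominator:** subjects with a non-missing baseline in that row's category (fasting, as the parameter is defined) and at least one post-baseline fasting result for that parameter.
- **Numerator:** those of them who meet the row's post-baseline criterion.
- **Missing baselines:** report these subjects separately, not as emergent.

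The change should be made before database lock, so that the rule is not settled by programming choice. It costs two sentences of SAP text and a change to one table program. The data are already collected, and fasting status is documented on the laboratory requisition. Denominators will be smaller and differ by row, so each must be shown in the table.
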